1. ISGA
2. EASI
3. % affected BSA calculation
4. Tape Stripping
5. Observer Reported Itch assessment (ORIA; ages 3 months - ≤ 11 years)
6. Patient Reported Itch Severity Scale (ages 6 years to ≤ 11 years old)
7. Observer Global Impression of Severity (OGIS; ages 3 months - ≤ 11 years)
8. Peak Pruritis NRS (Caregivers)
9. Children's Sleep Health Questionnaire (CSHQ; ages ≥ 4 to ≤ 11 years) OR BISQ (Brief Infant Sleep Questionnaire; ages 3 months - <4 years)
10. Medical Outcome Sleep Scale (MOS-Sleep; caregivers only)
11. Observer Global Impression of Change (OGIC)
12. Device Comfort Questionnaire (DCQ) / Observer Device Comfort Questionnaire (ODCQ)
13. Faces, Legs, Activity, Cry, and Consolability Scale (FLACC)
14. Dermatitis Family Impact Questionnaire (DFI; parent/guardian(s); ages 3 months- ≤ 11 years)
15. Children's Dermatology Life Quality Index (CDLQI; ages ≥ 4 - ≤ 11) OR Infants Dermatitis Quality Of Life Index (IDQOL; ages 3 months- <4 years)
16. Observer-Reported Patient-Oriented Eczema Measure (POEM; ages 3 months - ≤ 11 years)
17. Coordinator to retrieve and track return of devices.
18. Weigh and return compound or vehicle tube
19. Record participant disposition (completed study, left study early and reasons)

Participant Withdrawal/Stopping Rules

Participant comfort with the proposed procedures will be regularly assessed and no procedure will continue if the participant expresses discomfort or a desire to stop for any reason. If one Unanticipated Problem (UP) occurs, the study will be suspended until the investigators determine, with the BUMC/BMC IRB's input, that sufficient corrective measures can be put into place to allow it to proceed.

7. ASSESSMENTS

Below are the descriptions of the tasks chosen for this study; these brief summaries provide an overview of the range of task's objectives.

Tape Stripping:

Tape strips will be collected from participants from nonlesional and lesional skin at the time points outlined in the SoA. The area(s) to be used for tape stripping will be selected predose at V01 (Day -7) and documented. Index lesion selected as noted at V01, and documented on the Lesion/Non-Lesion Tape Stripping Site Identification Form, must be skin that is affected by atopic dermatitis and the lesional tape strip at V01 should be taken from skin that is adjacent to an affected skin lesion and must be part of the designated treatment area. Tape strips at subsequent visits should be taken from the same site as the initial index lesion, even if the lesion severity changes during the course of treatment.

Details on the processes for selection of lesional and non-lesional skin and collection and shipment of these samples can be found in the appendix.

Samples may be stored at a facility selected by the sponsor for a maximum of 10 years (or according to local regulations) following the last participant's last visit for the study and may be used for possible additional exploratory analysis only for this study, with all remaining samples being destroyed.

Biomarkers may include, but are not limited to target expression, nucleic acid analyses, and protein analyses. Samples may be analyzed for assessments related to inflammatory skin disease, the mechanism of action of crisaborole and/or responder/non-responder analyses.

All other assessments are included within the appendix section of this protocol.

8. SAFETY

8.1. Adverse Events

Any Adverse Events or Serious Adverse Events (defined below) encountered in the study will be monitored and reported to the BUMC IRB as per established procedures.

Adverse Event: Any untoward or unfavorable physical or psychological occurrence in a human participant, including any abnormal sign (for example, abnormal physical exam or laboratory finding), symptom, or disease temporally associated with the participant's participation in the research, whether or not considered related to the participant's participation in the research.

Serious Adverse Event: Any adverse event that:

- 1) Results in death
- 2) Is life-threatening (places the participant at immediate risk of death from the event as it occurred)
- 3) Results in inpatient hospitalization or prolongation of existing hospitalization
- 4) Results in a persistent or significant disability/incapacity
- 5) Based upon appropriate medical judgment, may jeopardize the participant's health and may require medical or surgical intervention to prevent one of the other outcomes listed in this definition.

Unanticipated Problem is defined as an event, experience or outcome that meets **all three** of the following criteria:

- is unexpected; AND
- is related or possibly related to participation in the research; AND
- suggests that the research places participants or others at a greater risk of harm (including physical, psychological, economic, or social harm) than was previously known or recognized.

Possibly related means there is a reasonable possibility that the incident, experience, or outcome may have been caused by the procedures involved in the research

Unexpected means the nature, severity, or frequency of the event is not consistent with either:

- the known or foreseeable risk of adverse events associated with the procedures involved in the research that are described in (a) the protocol-related documents, such as the IRB-approved research protocol, any applicable investigator brochure, and the current IRB-approved informed consent document, and (b) other relevant sources of information, such as product labeling and package inserts; or
- the expected natural progression of any underlying disease, disorder, or condition of the participant(s) experiencing the adverse event and the participant's predisposing risk factor profile for the adverse event.

8.2 Safety Review

Safety review for this study will be accomplished throughout the study and monitor all study activities identified in the schedule of activities. Risks to be monitored include: hypersensitivity, application site pain, application site discomfort, skin irritation, pyrexia, upper respiratory tract infection, diarrhea, cough, and any unknown risks or unanticipated problem identified in the performance of the study. This will be accomplished by study staff personnel as part of each visit activity, spontaneously reported by the caregivers, and monitored for all participants enrolled throughout the study. Specifically during each study visit, study staff will assess the level of skin irritation and participant reported discomfort (or AD flare up) from both the wearing of devices and/or subsequent topical application of crisaborole/vehicle. The Principal Investigator will be notified of any AEs immediately. All other reporting plans are outlined in section 8.3.

Signs of AD (based on % BSA) will be measured and evaluated throughout the study period on laboratory visits 3, 4, and 5 (days 2, 8, 15) by the study dermatologist. Participants whose BSA exceeds 40% at visits 3 and 4, will be instructed to terminate the use of vehicle/crisaborole and will be withdrawn from the study. We will monitor collected BSA percentages at each time point and their change from baseline. Participants will also be provided with a 24/7 phone number should they need to contact the laboratory after hours.

Appropriate documentation of any and all identified unanticipated or adverse events will be properly reported to the IRB including appropriate mitigation and reports for recommended changes, with unanticipated problems within 7 days. A document listing any identified safety related events will be maintained and monitoring of this list will be ongoing throughout the study as a means to track and review these events (accomplished by comparative analysis of each event in comparison to all other events throughout the study) to determine expectedness, relatedness, or suggestion of new risks that may have been identified. Other events will be documented, assessed and monitored by staff and investigators and reported at the time of continuing review. Monthly reviews of blinded adverse events will be

conducted to assess frequency of events, severity, seriousness, and relatedness to determine any potential trending study related items that may indicate a potential safety concern.

The data for adverse events (observed by study staff or spontaneously reported by caregivers) will be aggregated using descriptive statistics. Overlap of adverse events will be recorded.

Caregiver reported treatment-related adverse events will be recorded using MedDRA Version 24.1.

Severity of adverse events will be categorized as follows: Mild-Symptom(s) barely noticeable with no reported participant discomfort; Moderate- Symptom(s) reported as uncomfortable; Severe- Symptom(s) causing severe discomfort resulting in participant withdrawal. Relatedness of reported events will be categorized as follows: Unrelated- The event deemed to be clearly not study related; Possibly related- The event is temporally aligned with study activities but possibly may be due to another circumstance; Related- The event is temporally aligned to study activities with no alternative causes present.

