
The goal of this study is to more fully evaluate the rapid onset of night-time itch and scratch relief following treatment with Crisaborole in comparison to vehicle treatment in children with AD. Moreover, this study will assess the QoL and sleep within the associated caregivers.

Significance

Itch, night-time scratch and sleep are key symptoms experienced by patients with AD and impact not only the patient but the families of the patients with AD, particularly for young age children. Therefore, more fully understanding the cessation of the feeling of itch, action of scratch and improvements in sleep following treatment of Crisaborole (2% BID) would provide additional insight to the treatment profile. This study will specifically evaluate the rapid onset of itch and night-time scratch relief, improvement in sleep (both in the participant and their primary caregiver) and improvement in AD-inflammatory markers following crisaborole therapy twice daily (2% BID) in children 3 months to \leq 11 years old.

This study will also provide critical understanding of the ability of the accelerometry/actigraphy devices to measure drug-induced changes in scratching, movement and sleep quantity in children with symptomatic AD and quality of life in caregivers. It will also provide a physiological comparator for PRO/ObsRO assessments and ultimately enhance understanding of AD.

SCHEDULE OF ACTIVITIES

Period/Visit	Screening	V01 (Baseline)	V02	V03	V04	V05
Day	-28 to -7	-7	1	2	8	15
Window(days)	NA	+/- 3	+/- 3	+ 0.5	+/- 3	+/- 3
ENROLLMENT PROCEDURES						
Informed consent / assent	X	X				
Demographics, medical history including AD history/treatment	X	X				
Inclusion and exclusion criteria Review (both child and caregiver)	X					
Inclusion and exclusion criteria ‡ (both child and caregiver)		X				
Pregnancy test for female caregivers of child-bearing potential		X				
Wide Range Achievement Test 4 (WRAT-4; caregivers only)		X				
MEDICAL PROCEDURES						
Vital signs		X				
Height and weight		X				
ASSESSMENTS						
Investigator's Static Global Assessment (ISGA) (both child and caregiver at V01, only child thereafter)		X	X		X	X
Eczema Area and Severity Index (EASI)		X	X		X	X
% Body Surface Area (BSA)		X	X		X	X
Childhood Asthma Control Test (ages 4 to ≤ 11 years)		X				
Tape Stripping (Biomarker Assessment)**		X		X		X
PATIENT REPORTED/OBSERVER-REPORTED OUTCOMES (PROs/ObsROs)						

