 ** Nonlesional tape strips will be collected from an area of skin that is unaffected by atopic dermatitis at the baseline visit (V01). Lesional tape strips will be collected from skin adjacent to an atopic dermatitis lesion at the baseline visit (V01) and on Day 2 (V03) and Day 15 (V05).
 ° See Appendix for figure
 ***Participants may come in for an unscheduled visit as needed (i.e., to replace compound or vehicle, etc.)
 ****Devices will be optional for children participants who have active AD on location of device placement, with a minimum of at least one wrist device needed for enrollment

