5. STUDY PROCEDURES

The study will consist of a screening/baseline (in- laboratory) visit on Day -7 (V01), an in- laboratory visit Day 1 (V02), an in- laboratory visit on Day 2 (V03) for tape-stripping, and Day 8 (V04) for an assessment of the severity of the AD and a final in- laboratory visit on Day 15 (V05) for an assessment of the AD, tape-stripping, completion of ObsROs and return devices. Throughout the study, the participants and caregivers will wear accelerometry/actigraphy devices continuously (optional for those who have active AD on location of device placement, with a minimum of at least one wrist device needed for enrollment; devices may be removed for short periods of time for such things as the purposes of bathing, etc.). Enrolled participants will be randomly assigned to each arm of the study. Participants may come in for an unscheduled visit as needed (i.e., to replace compound, etc.). All in-person study activities, including informed consent and pregnancy testing, will be completed at the Laboratory for Human Neurobiology, [name]. All activities performed in the laboratory are accomplished in private rooms. Primary caregivers will be provided with ample time and a privacy curtain to change into a gown during assessment for exclusion of Atopic Dermatitis, and primary caregivers will accompany children during all activities to ensure participant privacy. All at-home study activities will be completed in the participants' home.

Phone Screening - Day-28 to -7 (~15 minutes):

- Verbal consent (including assent where applicable)
- Assign Participant ID (a sequentially assigned numerical ID used to identify participant on all study documents and in the electronic data capture [EDC] system)
- Screening demographics, medical history including AD history/treatment (includes, race, ethnicity, and gender)
- Eligibility screening (review of inclusion and exclusion criteria)

Baseline Visit 1 (V01)/Day -7 (+/- 3) – In Laboratory (~2 hours):

- Written Informed consent (including assent when applicable)
- Participants are randomly assigned to one of the two arms of the study
- Screening demographics (includes race, ethnicity, gender, and significant medical

history/treatment)

- Pregnancy test for female caregivers of child-bearing potential
- Wide Range Achievement Test 4 (WRAT-4)
- Eligibility Screening (Inclusion/Exclusion criteria)
- Vital signs
- Height and weight

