- Investigator's Static Global Assessment (ISGA) (scored by a dermatologist or a medically qualified individual who has been trained in the assessment; rater to be consistent throughout study)
- EASI assessment (scored by a dermatologist or a medically qualified individual who has been trained in the assessment; rater to be consistent throughout study)
- Calculate % body surface area (BSA) affected with AD
- Childhood Asthma Control Test
- Tape Stripping (Biomarker Assessment)
- Observer Reported Itch Assessment (ORIA; ages 3 months - ≤ 11 years)
- Patient Reported Itch Severity Scale (ages 6 years to ≤ 11 years old)
- Observer Global Impression of Severity (OGIS; ages 3 months - ≤ 11 years)
- Peak Pruritis NRS (Caregivers)
- Children's Sleep Health Questionnaire (CSHQ; ages ≥4-≤ 11) OR Brief Infant Sleep Questionnaire(BISQ; ages 3 months-<4 years)
- Medical Outcome Sleep Scale (MOS; caregivers only)
- Mobile Device Proficiency Questionnaire (MDPQ; caregivers only)
- Faces, Legs, Activity, Cry, and Consolability Scale (FLACCS)
- Dermatitis Family Impact Questionnaire (DFI; parent/guardian(s); ages 3 months- ≤ 11 years)
- Children's Dermatology Life Quality Index (CDLQI; ages ≥4-≤ 11 years) OR Infants Dermatitis Quality Of Life Index (IDQOL; ages 3 months-<4 years)
- Observer-reported Patient-Oriented Eczema Measure (POEM); ages 3 months – ≤ 11 years)
- The participant will be asked to don the accelerometry/actigraphy devices (coordinator will log dispensing) as follows: The participant will be provided the accelerometry/actigraphy devices immediately after completion of informed consent and will be trained. Devices will be optional for child participants who have active AD on location of device placement, with a minimum of at least one wrist device needed for enrollment.
 - Accelerometry
 - Children: Ages 2 years to ≤ 11 years; On R & L wrists
 - Caregivers: Ages 18 to 75 years; On R & L wrists
 - Actigraphy or accelerometry:
 - (Ages 3 months up to ≤ 11 years; On R & L wrists and R & L ankles for 3 months - <2 years; R & L wrists only for 2 – ≤ 11 years)

Out-of-Laboratory (At-Home) Assessments (Days -7–Day 1; Between Visits 1 & 2):

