1. ISGA
2. EASI
3. % affected BSA calculation
4. Children's Sleep Health Questionnaire (CSHQ; ages ≥ 4 to ≤ 11 years) OR BISQ (Brief Infant Sleep Questionnaire; ages 3 months - <4 years)
5. Medical Outcome Sleep Scale (MOS-Sleep; caregivers only)
6. Faces, Legs, Activity, Cry, and Consolability Scale (FLACC)
7. Dermatitis Family Impact Questionnaire (DFI; parent/guardian(s); ages 3 months - ≤ 11 years)
8. Children's Dermatology Life Quality Index (CDLQI; ages ≥ 4 - ≤ 11) OR Infants Dermatitis Quality Of Life Index (IDQOL; ages 3 months - <4 years)
9. Observer-Reported Patient-Oriented Eczema Measure (POEM; ages 3 months - ≤ 11 years)
10. In laboratory dose application training, including weight of the compound or vehicle tube
11. Drug Dispensing
12. Continuous accelerometry wear (Devices will be optional for child participants who have active AD on location of device placement, with a minimum of at least one wrist device needed for enrollment.)
13. Continuous actigraphy wear (Devices will be optional for child participants who have active AD on location of device placement, with a minimum of at least one wrist device needed for enrollment.)

Out-of-Laboratory (At-Home) Assessments (Days 1-15) (~15 minutes per day):

The purpose of the out-of-laboratory assessment is to evaluate wearable devices and ORIA/Patient Reported Itch Severity Scale in a home/routine setting (defined as the participant's routine environment/activities) while the child participant is receiving either crisabole or vehicle. Participants will be provided a fully-charged set of accelerometry devices for use at home.

1. Caregiver to complete ObsRO/PRO measurements as instructed:
 - Observer Reported Itch Assessment (ORIA; ages 3 months- ≤ 11 years)
 - Observer Global Impression of Severity (OGIS; ages 3 months- ≤ 11 years)
 - Peak Pruritis NRS (Caregivers)
 - Patient Reported Itch Severity Scale (Children 6- ≤ 11 years old)
2. At-home dosing (crisaborole or vehicle) in all affected areas except mouth, eyes, and vagina, per label
3. Continuous Accelerometry wear (Devices will be optional for child participants who have active AD on location of device placement, with a minimum of at least one wrist device needed for enrollment.)
4. Continuous Actigraphy wear (Devices will be optional for child participants who have active AD on location of device placement, with a minimum of at least one wrist device needed for enrollment.)

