Visit 3 (V03)/ Day 2 (+/- 12 hours) – In Laboratory (~30 minutes):

1. Collect Tape Stripping
2. Weigh tube of compound or vehicle

Visit 4 (V04) / Day 8 (+/- 3 day) In Laboratory (~1 hour):

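### Section 8.2 requires % BSA at Visit 3 and applies the 40% withdrawal rule there, but the Schedule of Activities and the Section 5 Visit 3 list contain no % BSA at that visit

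*Combined protocol and SAP*

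**What the plan says.** Section 8.2 (Safety Review) makes two statements about % BSA. The first is that signs of AD, based on % BSA, are measured "on laboratory visits 3, 4, and 5 (days 2, 8, 15) by the study dermatologist". The second is the rule that ends study treatment and leads to withdrawal: "Participants whose BSA exceeds 40% at visits 3 and 4, will be instructed to terminate the use of vehicle/crisaborole". The same section adds that the BSA percentages collected will be monitored at every time point, together with their change from baseline.

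The Schedule of Activities has a % BSA row with entries at V01, V02, V04 and V05. The V03 cell is empty.

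Section 5 (Study Procedures) introduces the on-treatment visits as "an in- laboratory visit on Day 2 (V03) for tape-stripping, and Day 8 (V04) for an assessment of the severity of the AD". Its visit lists include "Calculate % body surface area (BSA) affected with AD" at V01 and "affected BSA calculation" at each of V02, V04 and V05. The V03 list has two items: collection of tape strips, and "Weigh tube of compound or vehicle".

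**The concern.** A numeric withdrawal rule works only if the number is collected when the rule is to be applied. Section 8.2 applies its rule at two visits, and the two parts of the protocol that staff use to run a visit provide the measurement at only one of them. The rule is mandatory and applies to children from 3 months of age, so the texts should agree.

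The likely failure is simple. Someone working from the Schedule or the Section 5 list would finish V03 without a % BSA and would not know that one was due. The rule could then not be checked on Day 2. The first value obtained on treatment would be the one at V04.

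**Working it through.** There is no design figure to reproduce here. The check is a comparison of texts.

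**Inputs.** The % BSA row and visit header of the Schedule of Activities; the five visit lists in Section 5; and Section 8.2.

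**Step 1: visit numbering.** Section 8.2 gives day numbers (2, 8, 15) beside visits 3, 4 and 5. The Schedule header and the Section 5 headings also place V03 at Day 2, V04 at Day 8 and V05 at Day 15. So visit 3 in Section 8.2 is V03.

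**Step 2: is the empty cell real?** The tape-stripping row of the same table has entries at V01, V03 and V05. Its footnote independently gives baseline, Day 2 and Day 15. The columns are therefore aligned, and the empty V03 cell in the % BSA row is not a shift from reading the table. Section 5 separately omits % BSA at V03.

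**Step 3: % BSA by visit.**

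| Visit (nominal day) | Schedule | Section 5 list | Named for measurement in 8.2 | Named in the 40% rule |
|---|---|---|---|---|
| V01 (-7) | yes | yes | no | no |
| V02 (1) | yes | yes | no | no |
| V03 (2) | **no** | **no** | **yes** | **yes** |
| V04 (8) | yes | yes | yes | yes |
| V05 (15) | yes | yes | yes | no |

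Measurement visits in 8.2 without a scheduled % BSA: {V03, V04, V05} minus {V01, V02, V04, V05} = {V03}, or 1 of 3.

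Rule visits without a scheduled % BSA: {V03, V04} minus {V01, V02, V04, V05} = {V03}, or 1 of 2.

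**Step 4: could another entry supply the value?**

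- ISGA and EASI are also blank at V03 in the Schedule, so the EASI regional area scores are not available that day.
- The general statement in the Study Design that families return on Days 1, 2, 8 and 15 for assessments does not name % BSA.
- The check of irritation, discomfort and flare that Section 8.2 requires at each visit is not a % BSA.
- V02 comes at the end of the unmedicated acclimation week and is the visit at which study ointment is dispensed, so its % BSA is a pre-treatment value.

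**Step 5: timing.** If only the scheduled measurements are taken, the first on-treatment % BSA is at nominal Day 8 instead of Day 2, a difference of 8 - 2 = 6 days. The nominal interval between consecutive scheduled measurements, V02 to V04, is 8 - 1 = 7 days.

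**The case against.** The strongest reply is that Section 8.2 is itself operative protocol text. It requires the V03 measurement, and neither of the other texts forbids it. Nor are those texts exhaustive. Tube weighing is in the Section 5 lists but has no row in the Schedule. Adverse-event monitoring is in the Schedule but in none of the Section 5 visit lists. A missing entry is therefore weaker evidence that a procedure is not intended than it would be in a tightly kept protocol.

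This stands, and it limits the point to an omission from two working lists. It does not remove the point, because % BSA is listed explicitly at every other visit from V01 to V05. Section 8.2 also ties safety review to the activities identified in the Schedule, and then relies on one that the Schedule does not contain.

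The other reply is that little is exposed. V03 is nominally one day after dispensing, children enter with BSA below 40%, and other protection continues: checks at every visit, dermatologist monitoring, discontinuation for reactions, unscheduled visits and a 24-hour phone line. This also stands as a limit on the consequence, but none of these supplies the number that the rule uses.

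A reader might infer more than the documents support:

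- *That the texts cannot be followed together.* They can: staff can take a % BSA at V03 because Section 8.2 says so.
- *That V02 is a second mismatch, since Section 8.2 does not name it.* V02 is pre-treatment, Section 8.2 does not confine % BSA to visits 3 to 5, and its sentence on monitoring at every time point covers a value collected at V02.
- *That different sites would apply the rule differently.* Section 11.4 names one study location, and Section 5 places all in-person activities in one laboratory. The risk is that one team overlooks an entry.
- *That the rule can never operate because both visits must exceed the threshold.* The sentence can naturally be read as a check at each visit. The wording merits clarification while it is being edited, but it does not establish that stronger claim.

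**Conclusion.** The inconsistency is real and confined to V03. One of the two visits named in the withdrawal rule, and one of the three visits named for measurement in Section 8.2, has no % BSA in the Schedule or in its Section 5 list. If staff work from those lists, the 40% rule has no value to act on at Day 2, and the first on-treatment % BSA falls at nominal Day 8.

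This should be corrected because it concerns a mandatory stopping and withdrawal rule in children and the correction is nearly free. It does not show that children are unmonitored at V03. The number who might exceed 40% is unknown from the documents, so no effect on participants or on the trial's results is estimated. The conclusion rests on the current text of Section 8.2, the Schedule and Section 5, and on nominal visit days.

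**What to change.** Reconcile Section 8.2, the Schedule of Activities and the Section 5 visit lists so that every visit named in the withdrawal rule has a scheduled % BSA. While that sentence is being edited, make clear how the reference to the two visits is to be read. Which visits and which threshold apply is for the sponsor and investigator to decide.

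The cost is either a wording change in Section 8.2, or one Schedule entry with a matching line in the Section 5 list and the staff time for that assessment. Sample size, randomisation and the planned analysis are unaffected.
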